Data will be collected prospectively at scheduled time points according to a pre-established case report form (CRF) and stored in REDCap. Baseline evaluation contains characteristic information such as demographics, comorbidities, chronic medications, preoperative lab tests and clinical evaluations, planned surgical procedures, blood pressure, oxygenation saturation before fluid bolus administration. Intraoperative anaesthesia information to be collected include monitored vital signs, anesthetic choice and dose, parameters for mechanical ventilation (tidal volume, positive expiratory pressure delivered, FiO_2), use of open labeled fluids and the use of inotropic drugs and vasopressors, intraoperative complications, procedure characteristics, etc. Postoperative management including the analgesia regimen, transition from the operating room to postoperative anaesthesia care unit (PACU), intensive care unit (ICU), or ward, and any complications of research interest will be documented.

The observation periods start from randomization to 30 days after surgery. Participants are closely monitored until hospital discharge. After discharge, follow-ups are conducted through either in-person hospital visit or telephone calls. Any postoperative complications will be recorded. The observation periods start from randomization to 30 days after surgery. Patients who experience adverse events (AEs) will be monitored until recovery or at least until having any indication of improvement in AE symptoms. All unresolved AEs must be followed up until the outcome is determined, or at least until the final follow-up visit.

All data will be meticulously recorded in CRFs. The principal investigator at each site is responsible for data accuracy. Original documents and test results will be verified before producing electronic versions. Data quality will also be monitored through random checks against original CRFs. An independent Data and Safety Monitoring Board (DSMB), composed of a statistician, CRC, and anesthesiology expert, will oversee the safety and scientific validity of the study.

STUDY OUTCOMES

Primary Endpoint

The primary endpoint is the composite of postoperative complications that occur within 30 days following surgery. Specifically, these complications are

evaluated based on the modified Clavien-Dindo Classification, with those classified as \geq I (as detailed in Table 1) being considered.

Secondary Endpoint

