1. Incidence of hemodynamic instability, which is defined as a mean arterial pressure (MAP) dropping below 65 mmHg or decreasing by more than 20% from the baseline within 20 minutes after the induction of anesthesia.
2. Intraoperative consumption of vasopressors.
3. Length of postoperative hospital stay, calculated as the time interval between the index surgery and the patient's discharge from the hospital.
4. Rate of ideal postoperative recovery, determined as uneventful discharge within 5 days after surgery (without major complications, classified as \geq III according to the Clavien-Dindo classification, incision infection, and readmission);
5. Proportion of patients with Clavien-Dindo classification Grade IV complications, which is defined as life-threatening complications requiring ICU management, such as single organ dysfunction (including dialysis) or multiorgan dysfunction.

Exploratory outcomes

1. Each individual component of the composite primary endpoint (by organ system and by different Clavien-Dindo classification Grades)

2. 30-day all-cause mortality;
3. Incidence of unplanned ICU admission;
4. Incidence of unplanned reoperation;
5. Incidence of in-hospital complications;
6. Barthel index for activities of daily living (ADL) at 30 days after surgery.

Safety Outcomes

1. Incidence of acute kidney injury diagnosed by KDIGO criteria;³¹
2. Massive intraoperative bleeding (hemorrhage exceeds 1000 ml);
3. Episodes of intraoperative hypotension defined as SBP < 90 mm Hg or drop \geq 30% of baseline lasted for 5 min;
4. Episodes of hypertension defined as SBP > 180 mm Hg or rise \geq 30% of baseline lasted for 5 min;
5. Arrhythmia that consisted of bradycardia (heart rate < 40 beats per minutes), tachycardia (HR > 100bpm) or new onset of arrhythmia that require anti-arrhythmic drugs;
6. Airway hyper-responsiveness defined as a airway peak pressure > 40cm H₂O).

All outcomes will be discussed and evaluated by the endpoint assessment committee and documented as appropriate. All adverse events must be recorded in CRFs and documented. The reporting of SAE follows the

institutional requirement and local regulations.

STATISTICAL ANALYSIS PLAN

Scope of the Analysis plan

This Statistical Analysis Plan (SAP) presents the statistical consideration in design and analyses for COIN trial. The final manuscript will strictly follow this SAP.

Sample Sizes

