surgical procedures canceled after randomization, patients who withdrew their consent. The as-treated population is defined by the treatment that was actually received during the trial. This takes into account any deviations from the initially assigned treatment regimen, such as crossovers to the other treatments. The Per-Protocol (PP) population consists of all patients who received the assigned treatment without significant deviations from the protocol. Specifically, the analysis will be restricted to those who completed the full-term intervention as it was initially assigned. Participants with treatment interruptions will be excluded from the PP analysis. The exclusion list will be verified by the steering committee prior to lock of the database. Analyses conducted on these dataset will be treated as supplementary analyses.

General analysis Principles

The COIN trial is designed to assess the impact of preoperative colloid infusion on the occurrence of postoperative complications in surgical patients undergoing non-cardiac surgery with general anesthesia. The estimand is the difference in the incidence of postoperative complications as defined by higher than grade I Clavien-Dindo classification at 30 days after surgery between Colloid bolus administration versus crystalloid bolus administration, in patients undergo elective non-cardiac surgery under general anesthesia. The target population is patients experienced surgery procedure. The patients have the planned surgery canceled after randomization will be excluded from the

primary analyses.

In general, categorical variables are to be compared using χ^2 test or Fisher's exact test. Continuous variables will be compared via t-test or Wilcoxon's rank-sum test. Variable normality will be assessed either via the Shapiro-Wilk test or QQ-plots and residual plots. Variable transformation such as natural logarithm or square root will be applied where necessary, or non-parametric methods (such as Wilcoxon rank sum test) shall be applied.

For the analyses of primary, secondary outcomes, and the process measures, the following information will be presented:

- 📅 The number of patients included in each analysis, by treatment arm
- 📅 A summary statistic of the outcome (such as, number (%), mean (sd), media (IQR), etc), by treatment arm
- 📅 The estimated treatment effect
- 📅 A 95% confidence interval for the estimated treatment effect
- 📅 A two-sided P value

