For all analyses, a significance level of 5% will be used. Multiple comparisons will be conducted without Type I error correction and will be interpreted as exploratory.

Data Presentation and Baseline characteristics

Baseline characteristics will be summarized using descriptive statistics for whole patients cohort and for each treatment group by mean and standard

deviation or median and interquartile range for continuous variables, and the number, frequencies, and percent for categorical variables.

Durations According to Dates

For the indexed surgery, the date of randomization or admission to the intensive care unit corresponding to the surgery date will serve as day 1.

Take, for example, the calculation of the postoperative hospital stay (in days).

The formula is: (Discharge date from hospital - Date of index surgery) + 1

Exact dates will be tracked and documented.

Analysis of the primary endpoints

The primary endpoint, incidence of postoperative complications as defined by higher than grade I Clavien-Dindo classification at 30 days after surgery will be analyzed using Chi-squared test as crude analysis. Unadjusted risk ratios with 95% confidence intervals will be estimated by two-by-two table with the use of log-Normal approximation or other approximation/numeric methods as appropriate. The effect size will be expressed as risk differences (95% confidence intervals) will be estimated using Wald's likelihood ratio approximation test or other methods appropriate, with the number needed to treat as the reciprocal of the risk difference, rounded to the nearest integer.

Secondary Analyses of the primary endpoint

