The COIN trial is to evaluate whether colloid bolus infusion before anesthesia induction improves clinical outcomes compared to crystalloid bolus infusion in patients undergoing non-cardiac surgery under general anaesthesia. In clinical practice, in rare circumstance, surgery may be delayed or canceled, and the participant may not undergo surgery before the outcome is collected. Similarly, in rare instances, the surgery may be conducted under local anesthesia. These participants will be excluded and the left participants who undergo surgery will be analyzed as mITT datasets.

Protocol Deviations

The number and percent of patients with at least one protocol deviation will be summarized for each treatment arm. These include received wrong fluid, received wrong dose of fluid, or with infusion duration exceeds 15 min. These participants will be excluded and the left participants will be analysed as PP datasets.

Analysis of the secondary endpoints

Incidence of hemodynamic instability within 20min of anesthesia induction.

Incidence of post-induction hypotension will be analysed using a logistic regression model, adjusting for ASA grade, gender, age, NPO duration, fluid administration within 12 hours prior to surgery (y/n), history of hypertension.

Intraoperative consumption of vasopressors

Intraoperative consumption of vasopressors will be analyzed using a linear regression model, adjusting for ASA grade, gender, age, NPO duration, fluid administration within 12 hours prior to surgery (y/n), history of hypertension.

Length of postoperative hospital stay

Length of postoperative hospital stay will be analysed using a competing-risk time-to-event model, considering mortality as a competing risk for hospital discharge. The model will include adjustment for planned surgical procedure complexity grade, ASA grade, gender, age, baseline hemoglobin, and baseline creatinine. In case of convergence issues, singular matrix, or other numeric complexity, appropriate data transformation, or dimension reduction methods will be used.

For each treatment arm, we will present median and IQR for length of hospital stay for patients survived to hospital discharge. The number and percentage of patients survived to discharge and number and percentage of patients who died will also be reported.

Rate of ideal postoperative recovery within 5 days of surgery

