Prespecified subgroup analyses using formal tests of statistical interaction in a logistic regression model will be performed for the primary outcome to assess whether prespecified baseline variables modify the effect of treatment group on the primary outcome intervention differs among subgroup population. The subgroup analyses will be performed using the same model as for the primary endpoint. Independent variables will include study group assignment, the potential effect modifier of interest, and adding an interaction term between the two, aka the potential effect modifier and the treat arm. The presence of interaction will be tested using a likelihood ratio test comparing the subgroup

analysis model with interaction term, to the primary analysis model without interaction term. The test will be considered significant at the 5% level. A P value for the interaction will be reported. P values less than 0.1 will be considered potential interaction, while values less than 0.05 considered to a confirmed interaction. Non-linearity for continuous variables will be explored and analyzed using smoothed methods such as splines and preferably consider 3-5 knots using a locally weighted regression or partial effects plots.

Patients with complete outcome data will be included in the subgroup analysis. Within each subgroups, we will report summary statistics of the outcome by treatment arm, and a treatment effects and 95% confidence intervals. We will use a forest plot to display the effect of covariates. For presenting the continuous variables, they will be dichotomous for forest plot demonstration.

The pre-specified subgroups are:

- Participant center (1-7)
- age (continuous variable, and < 65 years vs ≥ 65 years)
- gender (male, female)
- BMI (continuous variable, and $< 24 \text{ kg/m}^2$ vs $\geq 24 \text{ kg/m}^2$)
- ASA classification (I, II ,III)
- Surgical procedure (abdominal, reproductive and urogenital system, musculoskeletal and connective tissue, breast & thyroid, facial and orthognathic surgery and ophthalmology, nervous system, other)
- Surgical complexity grade (minor, moderate, major, complex)

- NSQIP any complication risk (continuous variable)
- Inferior Vena Cava Collapsibility Index (continuous variable)
- Baseline SBP (continuous variable)
- NPO duration (continuous variable)
- Fluid administration at 12 hours prior to surgery

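### The haemodynamic instability model leaves out baseline MAP, which partly defines the endpoint and is already collected; this causes no bias but may cost some power

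*SAP*

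**What the plan says.** Under Secondary Endpoint, item 1 of the SAP, haemodynamic instability is "defined as a mean arterial pressure (MAP) dropping below 65 mmHg or decreasing by more than 20% from the baseline within 20 minutes" of induction. Under Analysis of the secondary endpoints the plan is: "Incidence of post-induction hypotension will be analysed using a logistic regression model, adjusting for ASA grade, gender, age, NPO duration", and the list ends with "fluid administration within 12 hours prior to surgery (y/n), history of hypertension". That makes six covariates, none of them a baseline pressure.

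Data Collection and Management includes among the baseline items "blood pressure, oxygenation saturation before fluid bolus administration". Baseline pressure is used elsewhere: Subgroup analyses lists "Baseline SBP (continuous variable") as a possible effect modifier, for the primary outcome only.

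On testing, the SAP says "For all analyses, a significance level of 5% will be used", and General analysis Principles asks for "A two-sided P value". Corrections for Multiple Testing treats everything beyond the single primary analysis as exploratory.

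**The concern.** One limb of the endpoint is calculated from the patient's own baseline MAP, so baseline MAP can be expected to predict the event. The model adjusts for history of hypertension, a yes/no stand-in, rather than for the measurement itself.

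Post-induction hypotension is the mechanism on which the SAP's Background rests the hypothesis, and the SAP plans to explore it as a mediator. If a useful predictor is left out, this comparison has less power than the data allow. Settling the covariate in advance also avoids a post hoc choice should baseline pressure differ between arms by chance. The SAP's provision for adding visibly imbalanced variables is written for the primary endpoint only.

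**Working it through.** **Plan's own figures.** The SAP gives no power, event rate or precision for this analysis, so there is no figure to reproduce. The sample size concerns the primary endpoint: 33% v 26% at two-sided 5% and 90% power needs 890 per arm, and 890/0.9 = 989, close to the stated 1010. What carries over is n = 2020 × 0.9 = 1818, two-sided 5%, and the 30-40% hypotension rate in the Background.

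**Where baseline enters.** With baseline B, the event occurs when post-induction MAP falls below T(B) = max(65, 0.8B). The limbs cross at 65/0.8 = 81.25 mmHg. If baseline MAP has mean 95 and SD 12 (assumed), the share above 81.25 is Φ((95 − 81.25)/12) = Φ(1.146), about 87%. At mean 84, SD 10 it is Φ(0.275), about 61%.

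**Why tracking matters.** Suppose post-induction MAP = a + sB + error with SD σ. Then P(event | B) = Φ((T(B) − a − sB)/σ). On the probit scale the slope in B is (0.8 − s)/σ above 81.25 and −s/σ below it. Two things follow:

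- The relation can be non-monotone, so a straight line may miss it.
- As s approaches 0.8, risk above 81.25 hardly depends on B, and adjustment has little to gain.

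**Simulation 1.** n = 1818, 600 replicates per scenario. Assumed, not in the SAP: baseline MAP 95 (SD 12); lowest post-induction MAP mean 80, SD 11; fluid effect 1.5 mmHg. Age and hypertension stand in for the SAP covariates in both models. Relative efficiency = (mean |z| with baseline MAP / mean |z| without)².

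| Correlation parameter | Control event rate | Mean z, without → with | Relative efficiency | Power | SE of log OR |
|---|---|---|---|---|---|
| 0.2 | 38.8% | 1.986 → 2.135 | 1.156 | 50.3% → 58.2% | 0.1009 → 0.1091 |
| 0.4 | 37.5% | 2.181 → 2.269 | 1.082 | 57.0% → 63.5% | 0.1010 → 0.1051 |
| 0.6 | 35.6% | 2.723 → 2.752 | 1.021 | 77.7% → 78.7% | 0.1023 → 0.1035 |
| 0.8 | 30.7% | 3.413 → 3.414 | 1.001 | 94.3% → 94.2% | 0.1077 → 0.1079 |

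These are for a linear term. Adding a quadratic term gives relative efficiencies of 1.163, 1.092, 1.040 and 1.024. With baseline 84 (SD 10) and post-induction mean 72, the linear term gains 1.001 (correlation 0.4) and 1.019 (0.6), and the quadratic 1.034 and 1.051. The Monte Carlo standard error of one power estimate is at most √(0.5 × 0.5/600) = 0.020, so the z ratio is the steadier guide.

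**Simulation 2.** n = 1818, 37% events, baseline 95 (SD 12), residual SD 11, 2 mmHg effect, a hypertension proxy in both models, 1,000 trials per slope. Adding a three-knot spline of baseline MAP gave:

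| Slope s | Power | Fall in variance of standardised risk difference |
|---|---|---|
| 0.2 | 78% → 83% | 11% |
| 0.3 | 79% → 82% | 9% |
| 0.5 | 83% → 84% | 4% |
| 0.7 | 87% → 87% | 1% |

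A further run at the same slopes, with about 39% events and both age and a hypertension proxy in each model, gave 76% → 82%, 79% → 82%, 83% → 83% and 85% → 84%. The variance of the standardised risk difference fell by 11%, 7%, 2% and 0%.

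**The case against.** The strongest reply is that nothing here is an error. The SAP prespecifies a valid model, and age, ASA grade and hypertension history carry part of the information in baseline pressure. The endpoint is exploratory and has no power target, and the gain rests on inputs the SAP does not give. All of that stands, and it limits the weight of the point. It does not remove the gain at weak tracking, which persists with age and hypertension proxies already in the model. The full six-covariate model was not simulated.

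Four stronger readings are tempting and are not supported:

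- **Bias.** A reader might infer that the treatment comparison is biased, or that chance differences in baseline pressure invalidate it. Allocation is randomised, so the omission causes no systematic bias, and the confidence interval already allows for chance imbalance.
- **Free precision.** A reader might expect a narrower interval for the odds ratio. In a logistic model the standard error of the conditional log odds ratio rises or stays level, as the first table shows. The gain comes from a larger conditional effect.
- **An endpoint that is purely a fall from baseline.** MAP below 65 mmHg alone also qualifies, and below a baseline of 81.25 mmHg that limit decides the event.
- **The vasopressor model.** It uses the same covariates, and one might extend the point to it. No gain was shown there.

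**Conclusion.** The point holds as a low-severity efficiency matter. A predictor built into the endpoint definition, and already measured, is missing from the model. Under the assumed inputs its inclusion is worth about 0 to 8 points of power, or a relative efficiency of about 1.00 to 1.17, depending mainly on how closely post-induction MAP follows baseline. No scenario showed a material loss. The unknowns are the baseline mean and SD, the degree of tracking and the size of the fluid effect; the SAP states none of them. Its use of baseline SBP in the primary-outcome subgroups shows that baseline pressure is available and thought relevant, but it does not make the SAP contradict itself.

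**What to change.** Before unblinding, add baseline MAP to the covariates of the haemodynamic instability model as a continuous variable with a three-knot restricted cubic spline. Use the same reading as in the endpoint definition and say that it is the pre-bolus value. The definition does not name the reading, and the SAP elsewhere refers to a pressure after the bolus, which treatment could affect.

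The cost is one prespecified covariate and no new data, since the 20% limb cannot be derived without a baseline MAP. The one downside is that the odds ratio becomes conditional on a further covariate. Reporting a standardised risk difference or risk ratio beside it deals with that, and is also where a gain in precision would show. Leave the vasopressor model as it is on this account.

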To account for potential confounders, the adjusted analysis of primary endpoint will use a logistic regression model, where the primary endpoint as the dependent variable and independent variables to include study group (colloid fluid bolus group vs crystalloid fluid bolus group), adjusting for the relevant confounders (planned surgical procedure complexity grade, ASA grade, gender, age, baseline hemoglobin, and baseline creatinine, NPO duration, fluid administration within 12 hours prior to surgery). Odds ratios (95% confidence intervals) will be reported; for those ORs may potentially be biased approximation for RRs, estimates will be obtained via either binomial regressions or converted using bootstrap methods. We will also develop a logistic regression model accounting for the above variables plus any baseline characteristics that appear on visual review to be potentially imbalanced between the study groups.

To account for the center effects, we will fit a mix-effect model with the primary outcome as dependent variable, including group assignment as a fixed effect and participant center (stratification variable) as a random effect. Potential confounders that included in the model are the same as the logistic regression model. Alternative method to use if mixed-effect models fail to reach convergence:

- Include participant sites as a fixed-effect instead of random effect.
- Remove the fixed effect for participant sites
- Adjust for age, hemoglobin, creatinine, fasting duration, etc as a single

continuous variable.

- Remove the covariates in prespecified order to see if convergence reached: gender, hemoglobin, creatinine, age, surgical complexity, ASA grade.

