Rate of ideal postoperative recovery within 5 days of surgery will be analysed using a logistic regression model, adjusting for planned surgical procedure complexity grade, ASA grade, gender, age, baseline hemoglobin, and baseline creatinine. Similar will be conducted for as above for cases of computing complexities.

Analyses of exploratory outcomes

Each individual component of the composite primary endpoint (by organ system and by different Clavien-Dindo classification Grades)

This will be analyzed using the same approach as for the analysis of the primary outcome above. Unadjusted Chi - squared test will be used.

Thirty day all-cause mortality

The expected event rate for this endpoint is extremely low. Thus, descriptive statistics will be used. Fisher exact test will be used to compare between group difference.

Incidence of unplanned ICU admission;

This outcome will be compared either using Chi-square test or Fisher exact test as appropriate depending on rate.

Incidence of unplanned reoperation

This outcome will be compared either using Chi-square test or Fisher exact test as appropriate depending on rate.

Incidence of in-hospital complications

This outcome will be compared either using Chi-square test or Fisher exact test as appropriate depending on rate.

Barthel index for activities of daily living (ADL) at 30 days after surgery.

The ADL score will be analyzed using a linear mixed model, with a random intercept for participant centers and adjusting for planned surgical procedure complexity grade, ASA grade, age, gender, baseline hemoglobin, and baseline creatinine. For any computation complexities, variable transformations or dimension reduction methods will be used.

Clavien-Dindo Grade IV - V complications within 30 days of surgery

Clavien-Dindo Grade IV - V complications within 30 days of surgery will be analyzed using a logistic regression model, adjusting for planned surgical procedure complexity grade, ASA grade, baseline hemoglobin, and baseline creatinine.

The expected event rate for this endpoint is lower than for other outcomes, thus we reduce the number of covariates that included in the model.

Analysis of Safety outcomes

Safety outcomes will be analyzed using the same method as the analysis of primary endpoints.

Interim analyses and stopping rules

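### The model for intraoperative vasopressor consumption omits planned surgical complexity grade, a baseline covariate already used in most of the SAP's other adjusted models; adding it is a small, nearly free gain in precision

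*SAP*

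**What the plan says.** The SAP's list of secondary endpoints names intraoperative consumption of vasopressors without a unit, a time limit, or scaling by weight or hour. Under Analysis of the secondary endpoints the model is: "Intraoperative consumption of vasopressors will be analyzed using a linear regression model, adjusting for ASA grade, gender, age, NPO duration", and the list ends with "fluid administration within 12 hours prior to surgery (y/n), history of hypertension". The paragraph just before it uses the same list for the early haemodynamic endpoint, which is confined to 20 minutes after induction: "Incidence of post-induction hypotension will be analysed using a logistic regression model, adjusting for ASA grade, gender, age, NPO duration".

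Planned surgical complexity appears elsewhere:

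- Adjusted logistic and mixed models for the primary endpoint (Secondary Analyses of the primary endpoint): "planned surgical procedure complexity grade, ASA grade, gender, age, baseline hemoglobin, and baseline creatinine, NPO duration".
- Length of stay: "The model will include adjustment for planned surgical procedure complexity grade".
- Ideal recovery: "using a logistic regression model, adjusting for planned surgical procedure complexity grade, ASA grade, gender, age, baseline hemoglobin, and baseline creatinine".
- The Barthel and Grade IV-V models (Analyses of exploratory outcomes).

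Planned procedures are recorded at baseline (Data Collection and Management). Complexity has four grades, minor to complex, and is among the pre-specified subgroup variables, apart from the modifiers that the SAP labels as collected after randomisation. Randomisation is stratified by centre only.

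**The concern.** The two haemodynamic endpoints share a covariate list but may not share a time frame. Hypotension in the first 20 minutes after induction has little to do with how extensive the operation will be. Drug use over the whole operation plausibly does, because a longer or larger procedure gives more occasion to use vasopressors. A list chosen for the first endpoint may therefore miss a useful predictor of the second.

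The SAP itself ranks complexity highly. If the mixed model for the primary endpoint does not converge, complexity is the second-to-last covariate to be removed and gender the first. The Grade IV-V model is deliberately cut down; it drops gender and age but keeps complexity. The vasopressor model keeps gender and age and has no complexity term, and no reason is given.

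At stake is the width of the confidence interval for one secondary endpoint. The SAP's background cites reduced vasoactive drug use as a benefit of preoperative fluid, so its precision has some interest.

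**Working it through.** **Figure to reproduce.** There is none. The SAP gives no standard deviation, effect size or power for vasopressor consumption; its sample size of 2020 concerns the primary endpoint. The check therefore compares the covariate lists and then gives a range under stated assumptions.

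**Step 1: the adjusted outcome models side by side.**

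| Model | Planned complexity included? |
|---|---|
| Primary endpoint, adjusted logistic and mixed | yes |
| Length of stay | yes |
| Ideal recovery | yes |
| Barthel index | yes |
| Grade IV-V complications | yes |
| Post-induction hypotension (20 minutes) | no |
| Vasopressor consumption | no |

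**Step 2: effect on precision.** Let R2 be the share of the residual variance, after the listed covariates, that complexity explains. In a 1:1 randomised comparison, adding the covariate to a linear model multiplies the standard error of the treatment effect by sqrt(1 - R2). The equivalent gain in sample size is 1/(1 - R2). All R2 values below are assumed.

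Evaluable patients per arm: 1010 × 0.9 = 909. For power, take the effect that would have 80% power without complexity, two-sided 5%: (1.960 + 0.842) × sqrt(2/909) = 0.131 SD. With adjustment, power is Φ(2.802/sqrt(1 - R2) - 1.960).

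| Assumed R2 | SE ratio | CI narrower by | Equivalent gain in patients | Power |
|---|---|---|---|---|
| 0.02 | 0.990 | 1.0% | 2.0% (19 per arm) | 80.8% |
| 0.05 | 0.975 | 2.5% | 5.3% (48 per arm) | 82.0% |
| 0.10 | 0.949 | 5.1% | 11.1% (101 per arm) | 84.0% |
| 0.20 | 0.894 | 10.6% | 25.0% (227 per arm) | 88.0% |

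**Step 3: cost if complexity is irrelevant.** Four grades need three indicator terms. With 2 × 909 = 1818 patients, three irrelevant terms explain by chance about 3/1817 = 0.00165 of the variance of the treatment indicator. The standard error then rises by a factor of 1/sqrt(1 - 0.00165) = 1.0008, that is, by less than 0.1%.

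**Step 4: check with awkward data.** A simulation (1818 patients, 400 replicates per setting) used skewed doses with many zeros. The dose scale and the share of treated patients both rose with complexity.

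| Dose scale, minor to complex | Partial R2 | Power without complexity | Power with complexity |
|---|---|---|---|
| 2-fold | 0.05 | 49.3% | 51.3% |
| 4-fold | 0.10 | 44.8% | 49.0% |
| 8-fold | 0.15 | 33.8% | 39.0% |
| no relation | 0.002 | 55.5% | 55.8% |

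The mean treatment estimate was practically the same with and without complexity (-0.304 and -0.303 in the 4-fold setting). The gradients are illustrative and come from no document.

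**The case against.** The strongest reply is that the SAP has pre-specified a complete and valid model, and that leaving a prognostic covariate out of a linear model in a randomised trial is a choice, not an error. The lists also follow a pattern: the two haemodynamic endpoints share one, and the recovery and complication endpoints draw on another. Nothing in the SAP promises complexity adjustment for every outcome. This stands, and it makes the point a suggestion for improvement rather than a contradiction.

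A reader might infer four stronger things that the SAP does not support:

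- **That this is the only adjusted model without complexity.** The hypotension model omits it too, reasonably for a 20-minute window. The primary analysis itself is an unadjusted chi-squared test; complexity enters only the secondary analyses of that endpoint.
- **That most variation in vasopressor use comes from the length and extent of surgery.** The SAP has no figure on this and does not relate complexity grade to duration. ASA grade and age may already carry part of the signal, so the increment may be small.
- **That the result would be biased.** Randomisation keeps the estimate without complexity unbiased.
- **That chance imbalance in case mix is a second harm.** It is the same noise, already reflected in the wider interval.

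The endpoint is also undefined as to unit, and the SAP allows transformation or non-parametric methods where needed. Neither the total-use reading nor the scale on which R2 would apply is certain.

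**Conclusion.** The omission is real and unexplained, and it sits less well with an endpoint covering the whole operation than with the 20-minute endpoint whose list it shares. The consequence is a possible loss of precision and nothing more. Its size cannot be computed from the SAP: over an assumed incremental R2 of 2% to 20% the confidence interval would narrow by about 1% to 10.6%, and the low end is entirely plausible. This rests on reading consumption as use over the whole operation and on complexity adding information beyond the listed covariates.

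The point is minor. The SAP treats everything beyond the single primary analysis as exploratory, and neither the sample size nor any stopping rule depends on this endpoint. It is worth making because the possible gain costs almost nothing and is credible only if specified in advance.

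**What to change.** Before unblinding, add planned surgical procedure complexity grade to the linear model for intraoperative vasopressor consumption, and keep the other covariates as listed. Use the planned grade, fixed before randomisation. Do not substitute actual surgery duration, which arises after randomisation and could be affected by the assigned fluid. The hypotension model can stay as it is.

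The cost is one added term in the SAP text and up to three degrees of freedom in about 1800 to 2000 patients. No new data are needed, since the grade is already used in other models.
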